Hypothesis. Relative to the materials-only control group, youth whose parents participate in ASSIST will have increased access to services and higher rates of employment, PSE, and social participation at 6-months and 12-months post-intervention.

Exploratory Aim 2a. We will examine whether ASSIST participation leads to enhanced goal attainment (as assessed by parents and youth with ASD), as well as better youth-reported quality of life and fit of employment/educational activities to the youth's skills and interests.

Exploratory Aim 2b. Using data collected 24-months and 30-months after intervention, we will examine whether treatment effects are maintained, strengthen, or wane.

Specific Aim 3. To examine which intervention targets (parent knowledge, advocacy skills, empowerment, advocacy activities) mediate the relations between ASSIST participation and youth outcomes of employment, PSE, social participation, service access, and goal attainment.

Hypothesis. In contrast to other intervention targets changed by ASSIST, parental empowerment will be the mechanism by which ASSIST participation leads to improvements in youth employment, PSE, social participation, service access, and goal attainment.

Exploratory Aim 4. To guide further adaptations of ASSIST, we will explore moderators of treatment response and barriers to participation in the intervention. We will explore factors that could relate to parents' ability to complete the ASSIST program and treatment

response, including: youth's intellectual functioning, pre- vs. post-high school exit, attendance at ASSIST sessions, socio-economic status, parental education, community size, family stress, and number of children with ASD in the family. We will also analyze qualitative data to inform future efforts to increase the accessibility of the ASSIST program for individuals with ASD.

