1.0 Study Procedures

All data collection will occur in years 2019-2023 as explained below:

- Enrollment for the project is expected to occur in years 1-2.
- Cohort 1 (C1) Intervention group will take ASSIST from February-August 2020 (IL and TN sites; includes COVID break) and August-November 2020 (WI sites)

- C1 Control group will take ASSIST September-November 2021 (TN and IL Sites) and January-March 2022 (WI Site)
- Cohort 2 (C2) Intervention group will take ASSIST from August-Nov 2020 (TN and IL Sites) and November 2020-February 2021 (WI site)
 - C2 control group will take ASSIST from February-April 2022 (TN and IL) and March-May 2022 (WI sites).

Note: Due to social distancing restrictions, the in-person intervention series that began in February 2020 was paused between Spring 2020 to Summer 2020 for Cohort 1 intervention groups (TN and IL). In response to continued pandemic regulations, ASSIST was moved to synchronous web-conferencing in Summer 2020, and this method was the mode of delivery for all remaining sessions and series at all sites (TN, IL, WI)

A comprehensive characterization of each participant's circumstances and family context will be completed by administering a battery of direct assessments and informant report measures during the baseline visit. This visit will include structured observations, psychological testing, structured interviews, and questionnaires/surveys. Note that some of the survey measures will be offered to participants as web-links to be filled out at home or at the lab if social distancing restrictions allow. Paper copies of all surveys will be available based on participant preference.

Follow-up data collection points (post-intervention, 6, 12, 18, 24, and 30 months) may take place online or over the phone, depending on participants' preference and the included measures to be collected for that time-point. We will also make alternate methods of data collection available to youth with ASD for the interview, including video/text/online chat, as some participants with ASD may be more comfortable answering questions via chat than over the phone or web conference. The table of measures included in the *Procedures for Enrolled Families* section of this protocol, shows the longitudinal measures follow-up schedule for parent and youth participants.

5. Procedures

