Effects of the Intervention (Aims 1 and 2): Generalized linear models accounting for repeated measurements over time will be used to estimate the effect of treatment group assignment on each of the outcomes. In modeling, outcomes will be considered at their key time-points with treatment group and the interaction of treatment with time serving as the main explanatory variables. Such a model will allow us to test for differences between treatment and control groups over time while accounting for heterogeneity among subjects at baseline. While the randomized block design should minimize confounding, we will adjust for site and sex to improve precision. Regarding the choice of statistical model, we will use ordinary multiple regression for truly continuous responses, logistic regression for binary responses, and for outcome scales that are not truly continuous or have heavy ties in some of their values, the proportional odds ordinal logistic model. The error structure of the model is assumed to be compound symmetric, and the validity of this assumption will be examined by computing Akaike Information Criteria against other common structures. **Mediation (Aim 3):** To assess direct and indirect effects of potential mediator variables, we will follow steps outlined by MacKinnon and

colleagues to establish mediation. Mediation models will be estimated using the “mediation” package in R. **Moderation (Exploratory Aim 4):** Modifiers of treatment effect over time will be considered by introducing interactions between modifiers and the treatment by time interaction. The model building and validation strategy will otherwise be the same as for Aims 1 and 2.

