Exploratory Aim 4: The starting point for multivariable modeling is an additive effects model. A purely additive model, even one with allowance for flexible nonlinear relationships, will not fit adequately if interactive or synergistic effects exist. Empirical search for interactions is unreliable because there are too many possible interactions (product terms) and frequently interactions found by intensive search techniques are spurious. Instead, interactions will be pre-specified based on subject matter knowledge and all results reported, regardless of statistical significance. Separate models will be fit for each moderator by including an interaction between the potential moderator and the treatment by time interaction. A similar model fitting strategy as outlined for Aim 1 and Aim 2 will be followed.

Though we are interested in examining the potential role of race/ethnicity as a modifier, it may be difficult to disentangle the effects of race/ethnicity from study site (as the geographic area of each site has a different racial/ethnic make-up). We will examine cross tabulation tables of the association between race/ethnicity and

site to determine how strongly they are associated. If possible, we will examine race/ethnicity as a moderator.

We will present any race/ethnicity results cautiously and clearly indicate the associations with site that could confound the observed associations.

As part of Aim 4, we will also use qualitative data analysis to code information gained from the open-ended questions regarding ways to adapt the intervention for youth with ASD. All interviews will be recorded and transcribed verbatim. With Atlas-TI, emergent coding⁸⁷ and constant comparative analysis will be used to identify themes in the transcripts⁸⁸.

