The power to detect mediation effects were made using the MedPow package in R^{82,83}. For the power calculation, we considered moderate associations between (1) VAP-T and the mediator ($r_{X,M}=0.3$), (2) Mediator and outcome, controlling for VAP-T ($r_{M,Y|X}=0.25$), (3) VAP-T and the outcome controlling for the mediator ($(r_{X,Y|M}=0.1)$ using a fixed sample size of 152 ($\alpha=0.05$). Under these assumptions, we have 83% power to detect the indirect effect of VAP-T on the outcome through the mediator.

Additional Analyses. In addition to these key analyses, we will conduct descriptive analyses to inform future research and development of the VAP-T. For example, we will carefully examine the attendance data to determine whether there is a number of sessions that seems necessary to benefit from the VAP-T, whether any particular sessions seem to be more important, and if accessing a greater proportion of sessions outside of the group format (i.e., at home, online) limits effectiveness. Analyses will include (but not be limited to) examining frequencies, medians, and means on intervention target scores for those who attended (vs. missed) each session and examining the distribution of outcome variables by the number of sessions in which content was accessed in the group format and by any format (in-person and online combined). We will also perform variable clustering and redundancy analysis by examining the correlation among the potential attendance predictors. We will work closely with our biostatistician to identify appropriate inferential statistics if these initial analyses appear informative to the further development of the VAP-T program.

BIBLIOGRAPHY

82. Cohen J. *Statistical power analysis for the behavioral sciences*. 2nd ed. Hillsdale, N.J.: L. Erlbaum Associates; 1988.

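### Exploratory Aim 4 lists session attendance among possible moderators, but controls have no sessions through 12 months, so the moderator model cannot be fitted for it

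*Protocol*

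**What the plan says.** **The list.** Protocol section 2, Exploratory Aim 4, has two purposes: "we will explore moderators of treatment response and barriers to participation in the intervention". It gives one list for both, covering completion of the programme and response to treatment. The list includes "attendance at ASSIST sessions, socio-economic status, parental education". Its other items are the youth's intellectual level, whether the youth has left high school, stress in the family, the size of the community and how many children in the family have ASD. Every item except attendance can be measured before randomisation.

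**The model.** Protocol section 8: "Modifiers of treatment effect over time will be considered by introducing interactions between modifiers and the treatment by time interaction". SAP, Exploratory Aim 4: "Separate models will be fit for each moderator by including an interaction between the potential moderator and the treatment by time interaction". The SAP adds that interactions are pre-specified and that all are reported, significant or not. It discusses race/ethnicity as a moderator but gives no full list of its own.

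**The controls.** The protocol's background section says that controls receive the written materials without the group training, which they may take at the end of the study. The SAP's power section ties Aims 2 to 4 to 152 participants (76 per arm) followed to 12 months.

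**The separate attendance work.** Under Additional Analyses, the SAP will look at "whether there is a number of sessions that seems necessary to benefit from the VAP-T". It compares families who attended each session with those who missed it, and summarises outcomes by number of sessions accessed in the group format and "by any format (in-person and online combined"). It calls this descriptive and leaves inferential methods for later. On delivery after the pandemic pause, Protocol 1.0 Study Procedures says that "this method was the mode of delivery for all remaining sessions and series at all sites (TN, IL, WI").

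**The concern.** A moderator analysis asks whether the randomised contrast differs between kinds of family. That requires a characteristic that is defined in both arms and fixed before allocation. Attendance is neither. It arises after randomisation, and through 12 months it varies only in the ASSIST arm. Software given the stated model would drop the redundant terms, and the remaining attendance × time coefficient could be reported as moderation. It would in fact compare more engaged with less engaged families.

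Exploratory Aim 4 is meant to guide later adaptations of the programme. At stake is whether family engagement is read as an effect of dose and, on one reading of the format variable, whether site and cohort are read as an effect of format.

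**Working it through.** **The plan's own Aim 4 figure.** The SAP states 80% power for a 0.42 SD modification at r = 0.2. The base case reproduces: a two-sample t test with 76 per arm detects 0.457 SD, against the stated 0.46. The 0.42 does not. Four cells of 38 (a 50:50 binary moderator, assumed) give 2 × 0.457 × √(1 − 0.2²) = 0.90 SD. A continuous moderator gives (1.960 + 0.842) × 2/√152 × √0.96 = 0.45 SD per SD. That is a separate matter, and nothing below depends on it.

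**Step 1: control attendance through 12 months.** Dates are from Protocol 1.0 Study Procedures. The 12-month point is counted from the end of the matching intervention series.

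| Group | ASSIST series ends | 12-month point | Control series starts |
|---|---|---|---|
| Cohort 1, TN/IL | Aug 2020 | Aug 2021 | Sep 2021 |
| Cohort 1, WI | Nov 2020 | Nov 2021 | Jan 2022 |
| Cohort 2, TN/IL | Nov 2020 | Nov 2021 | Feb 2022 |
| Cohort 2, WI | Feb 2021 | Feb 2022 | Mar 2022 |

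Every control series starts after the 12-month point. With visits on time, control attendance is zero by design over the Aim 4 horizon.

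**Step 2: controls coded 0.** Let T be treatment (0/1), A attendance and f(t) any function of time, splines included. If A = 0 whenever T = 0, then A × T = A and A × T × f(t) = A × f(t). For baseline and two follow-ups the columns are 1, t1, t2; T and its two time products; A and its two; A × T and its two: 12 in all. With 76 per arm the matrix has rank 9, so three columns are redundant: A × T and its two time interactions. If control attendance varied, the rank would be 12.

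**Step 3: controls coded missing.** Their rows leave the model, T is constant, and no treatment interaction exists.

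**Step 4: how far a within-arm comparison can mislead.** The correlations here are assumptions, and attendance is given no true effect.

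- *Correlation version.* An engagement factor correlated c with both attendance and outcome gives a spurious correlation c². For c = 0.3, 0.4, 0.5 this is 0.09, 0.16, 0.25. With n = 76, Fisher's z gives a rejection rate of about Φ(√73 × atanh(c²) − 1.96) = 12%, 28%, 59%.
- *High versus low attenders.* Motivation correlates 0.7 with latent attendance and ρ with outcome. The expected difference is 2√(2/π) × 0.7 × ρ = 1.117ρ. For ρ = 0.2, 0.3, 0.5 this is 0.22, 0.34, 0.56 SD. In simulation a nominal 5% test rejected 15%, 31% and 70% of the time, and 5% when ρ = 0.

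For scale, a 38 versus 38 split within the arm detects 0.65 SD at 80% power.

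**Step 5: format.** In-person sessions took place only in Cohort 1 at TN and IL, before the pause. At 30 per site and 1:1 allocation that is 15 + 15 = 30 of the 90 planned ASSIST families. If live web sessions were coded as outside the group format, all group-format exposure would lie in those families, and format could not be separated from site, cohort and pandemic timing. If live web sessions count as group format, this problem does not arise.

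**The case against.** The strongest reply is that nobody has planned this interaction. It follows only from putting the Aim 4 list together with the general rule. The list also serves barriers to participation, where attendance belongs. Where the protocol names its key moderators outright, in the Innovation and Randomization text, they are intellectual disability and high-school status. The SAP handles attendance separately and descriptively. All of this is fair, and it lowers the severity. It does not remove the defect: the list ties its items to treatment response as well as completion, the rule covers each moderator, and no text takes attendance out.

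The Step 4 rates also need restraint. A reader might take 12%, 28% and 59% as the false-positive rate of a planned test. Neither document plans that test. In the Aim 4 model the surviving term is attendance × time, from which an engagement factor that shifts the outcome equally at every wave would drop out. Only engagement related to change would bias it.

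A reader might also infer that the SAP's format comparison is confounded as it stands. The protocol describes ASSIST as a group training held by web-conference, so live web sessions can be read as group format. The SAP's wording is ambiguous, not wrong.

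Finally, a complier-average analysis may look like the answer to the dose question. Randomised assignment is a single binary instrument. It yields one average effect and cannot show how many or which sessions matter. Its exclusion restriction is threatened by benefit from attendance below any threshold, by content accessed at home, and by unblinded parents reporting on themselves.

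**Conclusion.** The point holds and is minor. Through 12 months the stated moderator model cannot be estimated for attendance under either coding. What can be estimated is a non-randomised contrast within about 76 ASSIST families. This follows from the design and needs no effect-size assumption, only that control series ran on the published dates and 12-month visits were on time (the margin is about one month in two of the four groups).

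A reader might infer that only the ASSIST arm can ever attend. Controls may attend later, so at 18 to 30 months the columns need not be aliased. Attendance would still be post-randomisation, and at a different calendar time in each arm. A reader might also infer that the trial's main conclusions are at risk. They are not: Aim 4 is exploratory and Aims 1 to 3 do not use attendance. The size of any engagement bias is unknown; the Step 4 figures only illustrate it.

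**What to change.** 1. In Exploratory Aim 4 and the SAP, separate moderators from participation factors. Enter only baseline variables in the treatment-by-time interaction, and analyse attendance as an outcome, with baseline predictors of completion.
2. Under Additional Analyses, label the attended-versus-missed and number-of-sessions summaries as within-arm, non-randomised associations that cannot establish a necessary dose.
3. Define format as live group session (in person or web) versus content accessed alone.
4. Optionally, add a complier-average effect with randomised assignment as the instrument, as a sensitivity analysis only, with its assumptions and the limits above stated.

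Items 1 to 3 change wording and coding and need no new data. Item 4 costs one extra analysis, with a wider interval than an as-attended comparison.

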1.0 Study Procedures

All data collection will occur in years 2019-2023 as explained below:

- Enrollment for the project is expected to occur in years 1-2.
- Cohort 1 (C1) Intervention group will take ASSIST from February-August 2020 (IL and TN sites; includes COVID break) and August-November 2020 (WI sites)

- C1 Control group will take ASSIST September-November 2021 (TN and IL Sites) and January-March 2022 (WI Site)
- Cohort 2 (C2) Intervention group will take ASSIST from August-Nov 2020 (TN and IL Sites) and November 2020-February 2021 (WI site)
 - C2 control group will take ASSIST from February-April 2022 (TN and IL) and March-May 2022 (WI sites).

Note: Due to social distancing restrictions, the in-person intervention series that began in February 2020 was paused between Spring 2020 to Summer 2020 for Cohort 1 intervention groups (TN and IL). In response to continued pandemic regulations, ASSIST was moved to synchronous web-conferencing in Summer 2020, and this method was the mode of delivery for all remaining sessions and series at all sites (TN, IL, WI)

A comprehensive characterization of each participant's circumstances and family context will be completed by administering a battery of direct assessments and informant report measures during the baseline visit. This visit will include structured observations, psychological testing, structured interviews, and questionnaires/surveys. Note that some of the survey measures will be offered to participants as web-links to be filled out at home or at the lab if social distancing restrictions allow. Paper copies of all surveys will be available based on participant preference.

Follow-up data collection points (post-intervention, 6, 12, 18, 24, and 30 months) may take place online or over the phone, depending on participants' preference and the included measures to be collected for that time-point. We will also make alternate methods of data collection available to youth with ASD for the interview, including video/text/online chat, as some participants with ASD may be more comfortable answering questions via chat than over the phone or web conference. The table of measures included in the *Procedures for Enrolled Families* section of this protocol, shows the longitudinal measures follow-up schedule for parent and youth participants.

5. Procedures

Eligibility Screening Procedures: Staff at each site will inform potential participants of the study, when subjects contact the site (via email, phone and/or interest form survey) in response to recruitment efforts. As soon as the potential parent participant is available, staff at each site (depending on the state of residence of the subject) will conduct a telephone screening interview with the subject's verbal permission. All screening phone interviews will be completed with parents (never with a youth with ASD) using the phone script electronically and/or in paper/pencil. During the eligibility screening phone call, the study team member will administer the Social Communication Questionnaire (SCQ – Rutter, Bailey, Kazak, Lord & Pickles, 2003) to the parent / LAR (as one of the eligibility inclusion criteria for the study is that the score on the SCQ Lifetime Questionnaire is 15 or higher; although in rare circumstances, a score between 10-14 may not prevent a family from participating in the study – this will be evaluated by the PI on a case by case basis). The SCQ offers a quick and easy way to screen for autism spectrum disorders by asking caregivers 40 yes/no questions about the child's communication skills and social functioning.

If after the telephone screening, the STM determines that the family is not eligible to participate in the study, we will explain this to the parent. We will destroy any record of the parents' responses to the screening phone call questions, unless the family says they would like to be contacted for future studies. For reporting purposes only, we will document the reason for ineligibility of the screened family (e.g. the son/daughter never received a diagnosis of an ASD) in a "recruitment tracking document" that will not include any of the screened subject's PHI or responses.

Procedures for enrolled families: For each participating family, the testing battery at baseline will be the most extensive one. After that, the number of administered instruments will vary depending on the specific follow-up data collection time. Similarly, depending on the number and type of instruments to be collected during the follow-up data collection times; study staff at each site will collect the data via: phone interview or teleconference, REDcap survey, and/or paper protocols; depending on the family's preference.

Youth measures

Test / Procedure	Baseline (T0)	12-m FU (T3)	30-m FU (T6)
Youth (Baseline)	T0	T3	T6
Autism Diagnostic Observation Schedule: (ADOS-2; Lord et al., 2012) A semi-structured standardized observational assessment of social interaction and communicative skills that was designed as a diagnostic tool for identifying the presence of autism. It is organized into four modules, which are distinguished by their appropriateness for use with individuals functioning at different developmental levels, ranging from nonverbal children to highly fluent adults. Each module provides a set of behavioral ratings in five domains: Language and Communication, Reciprocal Social Interaction, Play or Imagination/Creativity, Stereotyped Behaviors and Restricted Interests, and Other Abnormal Behaviors. We will mainly use Module 3 and 4 (dedicated to verbally fluent teenagers and adults), and Module 1 and 2 (that can be used for non-verbal adults or less verbal adults). The scoring algorithm provides cutoffs that can be used to discriminate between a diagnosis of autism, autism spectrum, or non-spectrum. The ADOS will be administered to participants with ASD. It will be administered by trained research staff. All ADOS-2 administrations will be video-recorded with the participant's explicit consent. Note: After data collection was moved online due to social distancing restrictions, the ADOS-2 was no longer required as a diagnostic measure for remaining participants.)	X		

Wechsler Abbreviated Scale of Intelligence (WASI-II, Wechsler, 2011): Provides a brief, reliable measure of cognitive ability for use in clinical, educational, and research settings. It is comprised of 4 subtests that yield a verbal intelligence quotient, a performance quotient, and an overall intelligence quotient. (Note: After data collection was moved online due to social distancing restrictions, the research staff used 2 of the subtests which were able to be administered virtually. The other 2 subtests were not administered to remaining participants.)	X		
Youth Measures (Longitudinal)	T0	T3	T6
Vocational - educational activities interview: ([name] & Seltzer, 2012) this instrument gathers information on vocational, educational, and other daytime activities. A trained research staff member will deliver this brief interview to gather information on current and previous high school employment, secondary education and post-high school vocational placements.	X	X	
Goal identification (baseline) / Goal Attainment (FUs): Our team developed a goal bank that includes goals that fall into 5 categories: Employment & Post-Secondary Education, Daily living, Social and Spirituality, Healthy Living, and Safety & Security. This goal bank is a start point to help families think about a vision for how their family member will live their life as an adult. The parent will select 5 potential goals from the goal bank, and work with a study team member to customize the selected goals during the baseline visit. After that, the youth will review the customized goals and/or select three of them that he/she is interested in (or create new customized goals if none of the goals the parent customized are of the youth's interest). Goals that are specified during this identification session will be scaled using Goal Attainment Scaling (GAS). GAS is an individualized outcome measure to calculate the extent to which specific goals are met by an individual. Goal selection will vary from participant to participant, but the goal scale will be standardized to measure goal attainment consistently across	X	X	

participants. During FUs, study staff will reach out to the youth participant and check in on goal progress status.			
Self-Determination Inventory System Adult (SDIS – ADULT): The SDIS (Shogren et al., 2017) is a 22-item survey that asks adults how they feel about their ability to be self-determined; make choices, set and go after goals, and make decisions. Participants use a sliding scale to indicate their level of agreement with various statements related to self-determination.	X	X	X
Transition Empowerment Scale (TES): Adapted from the Family Empowerment Scale (FES; Koren, DeChillo, & Friesen, 1992) to measure adolescents and young adults with disabilities' perceived empowerment during transition planning. This modified 31-item instrument enables young adults to self-report how empowered they feel to manage their day-to-day life, understand the services available to them, and advocate for themselves and for other adolescents with disabilities. The young adult rates statements from 1 (Not True) to 5 (Very True) to indicate how much each one applies to him/her. The scale captures the young adult's view of their own empowerment at one point in time by measuring both the level of empowerment and how it is expressed.	X	X	X
Satisfaction with Life Scale (SLS): the SLS (Diener et al., 1985) is a short 5-item measure of an individual's subjective quality of life. Participants rate their agreement with 5 statements on a 7-point scale, from 1 (Strongly Disagree) to 7 (Strongly Agree).	X	X	X
Open-Ended Questions: Participants give their opinions on future intervention programs for people with ASD			X

Parent measures

Test/ procedure	Baseline e (T0)	Post- test (T1)	6-m CI (T2)	12-m FU (T3)	18-m CI (T4)	24-m CI (T5)	30-m FU (T6)
Youth /Parent Characterization (Baseline)	T0	T1	T2	T3	T4	T5	T6
Demographics and medical history: Demographic information for NIH reporting, as well as diagnostic and treatment information.	X						
Vineland 3- Comprehensive Interview form: (Sparrow, Cicchetti & Saulnier, 2016) a measure of adaptive behavior functioning. It is administered as a brief interview to parents or caregivers, and yields standard scores and age equivalents in the domains of communication, social, daily living skills and overall adaptive functioning.	X						
Social Responsiveness Scale, Second Edition: (SRS- 2, Constantino & Gruber, 2012) A 65 item parent-report scale measuring the presence and severity of social impairment as it relates to Autism Spectrum Disorder. The measure is sensitive enough to quantify severity within the spectrum and differentiate between ASD and other disorders. The SRS-2 generates a total score as well as scores for each of its five subscales: social awareness, social cognition, social communication, social motivation, and restricted interests and repetitive behavior. The SRS-2 parent- report will be given to parents of all participants with ASD.	X						
Participants will complete the ABCL or the CBCL, depending	X						


on their youth's age. Parents of youth ages 16-17 will complete the CBCL, and parents of youth age 18 and over, the ABCL.
 
Child Behavior Checklist 6-18 (CBCL; Achenbach & Rescorla, 2001) A 113-item scale designed to be rated by parents of children aged 6-18. The questions are scored on a three-point Likert scale (0=absent, 1=occurs sometimes, 2=occurs often). The time frame for item response is in the past six months.
 
Achenbach Adult Behavior Checklist 18-59: (ABCL; Achenbach & Rescorla, 2003) A 118-item scale designed to be rated by parents of adult children aged 18 to 59. The ABCL is based on a multi-factor model, for which domains of withdrawn, somatic problems, and anxious/depressed are indicators of a more general "Internalizing" factor, while delinquency and aggression domains are indicators of the "Externalizing" factor (Tenneij & Koot, 2007).
	

Coping Orientation to Problems Experienced (COPE) Inventory: (Carver, Scheier, & Weintraub, 1989) multidimensional coping inventory to assess the different ways in which people respond to stress. Participants rate 60 items with potential responses to stress on a scale from 1 (I usually don't do this at all) to 4 (I usually do this a lot).
	X

Parent Repeated measures (Longitudinal)	T0	T1	T2	T3	T4	T5	T6
Family Empowerment Scale: (FES; Koren, DeChillo, & Friesen, 1992) developed specifically to assess empowerment in families with children with emotional disorders. The FES consists of 34 items with responses on a Likert scale ranging from 1 (Not true at all) to 5 (very true).	X	X ^T		X ^T	X		X
Parent Advocacy Skills and Comfort (ASC) & Knowledge measure: Both of these measures were developed by the ASSIST team. The Advocacy Skills and Comfort (ASC) measures the degree to which parents feel comfortable and skilled in advocating for their son/daughter with ASD. The assessment comprises 10 items, on which participants respond on a 5-point Likert scale (1 = not at all; 2 = below average; 3 = average; 4 = good; 5 = excellent). The Knowledge measure serves to examine the extent of parents' knowledge about the adult service system through a scale developed for this project (based on a measure developed to evaluate the VAP-T; Burke, Goldman, Hart, & Hodapp, 2016). Each response will be coded as either "correct" (1) or "incorrect" (0), with potential scores ranging from 0 to 22 and higher scores equaling greater knowledge of the adult disability service	X	X ^T		X ^T	X		

system. This measure was piloted among a group of parents of older sons and daughters with ASD to ensure that floor and ceiling effects were avoided.							
Vocational - educational activities interview: ([name] & Seltzer, 2012) A trained research staff member will deliver this brief interview to gather information on current and previous high school employment, secondary education and vocational placements that the son/daughter is/was involved in.	X		X ^P	X ^P		X	X
Service Access questions Interview (NLTS2 questions and team-developed questions): The National Longitudinal Transition Study-2 (NLTS2) collected data over 10 years from parents, youth, and schools and provided a national picture of the experiences and achievements of young people as they transition into early adulthood. For the proposed research, we will use some of the questions developed for the NLTS2 concerning service access for youth with ASD, and will supplement them with questions developed for our research about specific types of services (e.g., Medicaid, etc.). These questions will be answered by parents using a semi- structured interview format	X		X ^P	X ^P		X	X
Parent Advocacy Activities Measure: ([name] et al., 2017) this instrument has 16 items that measures how frequently	X			X ^P			X

parents spend time in advocacy activities for their son/daughter with ASD.						
Goal identification (baseline) / Goal Attainment (FUs): Our team developed a goal bank that includes goals that fall into 5 categories: Employment & Post-Secondary Education, Daily living, Social and Spirituality, Healthy Living, and Safety & Security. This goal bank is a start point to help parents think about a vision for how their family member will live their life as an adult. The parent will select 5 potential goals from the goal bank, and work with a study team member to customize the selected goals during the baseline visit. After that, the youth will review the customized goals and/or select three of them that he/she is interested in (or create new customized goals if none of the goals the parent customized are of the youth's interest). Goals that are specified during this identification session will be scaled using Goal Attainment Scaling (GAS). GAS is an individualized outcome measure to calculate the extent to which specific goals are met by an individual. Goal selection will vary from participant to participant, but the goal scale will be standardized to measure goal attainment consistently across participants. During FUs, study staff will reach out to the parent participant and check in on the youth's goals' progress status.	X		X ^s			

Social Participation and employment correlates: The National Longitudinal Transition Study-2 (NLTS2) collected data over 10 years from parents, youth, and schools and provided a national picture of the experiences and achievements of young people as they transition into early adulthood. For the proposed research, we will use some of the questions developed for the NLTS2 concerning parent's social participation. In addition, we are including some questions developed to measure employment and social participation ([name], Adams, Bishop, 2017).
	X			X ^s				X

Satisfaction with Life Scale (SLS) - proxy report regarding son/daughter: the SLS (Diener et al., 1985) is a short 5-item measure of an individual's subjective quality of life. The SLS scale allows participants to integrate and weigh these domains in whatever way they choose. Participants rate their agreement with the 5 statements on a 7-point scale, from 1 (Strongly Disagree) to 7 (Strongly Agree).
	X			X ^s				X

Depression, Anxiety, Stress Scales – 21 items (DASS-21): (Lovibond & Lovibond, 1995) set of three self-report scales designed to measure the emotional states of depression, anxiety and stress. Each of the three DASS-21 scales contains 7 items, divided into subscales with similar content. The depression scale assesses dysphoria, hopelessness,
	X			X				X

devaluation of life, self-deprecation, lack of interest / involvement, anhedonia and inertia. The anxiety scale assesses autonomic arousal, skeletal muscle effects, situational anxiety, and subjective experience of anxious affect. The stress scale is sensitive to levels of chronic nonspecific arousal. This scale assesses difficulty relaxing, nervous arousal, and being easily upset/agitated, irritable/over-reactive and impatient.
								

General Life Events: assesses milestones, changes, and challenges that may have occurred in an individual's life within the past year. The parent participant indicates whether he/she, his/her spouse, and his/her children have experienced any of the 22 listed life events (e.g. marriage, divorce, moving to a new home, etc.) or other (item 23).
	X			X				

Disability Connectedness: This measure assesses the extent to which a participant relates to his/her local disability community. The instrument consists of 10 items. Participants respond on a 5-point Likert scale (1 = not at all; 2 = slightly; 3 = to some extent; 4 = quite a bit; 5 = very much so).
	X			X				X

Parent-Child Relationship: this 10-item instrument (Bengtson & Schrader; 1982) measures a parent's perceptions of how positive his/her relationship is with his/her child. Responses range
	X			X				

from 1 (Not at all) to 6 (Extremely).						
Parent expectation questions from NLTS-2 (same for all): The National Longitudinal Transition Study-2 (NLTS-2; Sanford et al., 2011) documented the experiences of students nation-wide as they made their transition to adulthood. The NLTS-2 provides insight into the involvement of families in the educational development of high school-aged youth with disabilities. The present study uses a modification of the parent expectations questions from the NLTS-2, Parent Expectations, which asks parents to speculate about their youth's future at the end of and after high school. This measure includes items about the youth's potential employment, living situation, and postsecondary education.	X			X		X
